11.3 Analysis Populations

The following analysis populations are defined for the study: Intent-to-Treat (ITT), modified Intent-to-Treat (mITT), Per-Protocol (PP) and Completed Cases (CC). The primary safety analysis will be performed on the ITT population. The primary effectiveness analysis will be performed on mITT population.

- Intent-to-Treat: The Intent-to-Treat population includes all enrolled participants as defined in Section 5.3 regardless of whether or not the participant received the full treatment.
- Modified Intent-to-Treat: The mITT population consists of the ITT population participants who received the target treatment (at least 6 cm of duodenum treatment) and that have at least one post-treatment follow-up.
- Per-Protocol: The Per-Protocol population is a subset of the mITT population and includes all participants who received the target treatment, do not have any major eligibility violations, and maintained stable glucose-lowering medications for 24 weeks post procedure.

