11.4.3 Secondary Endpoint Analysis

Secondary endpoints are summarized in Section 3. The primary analysis of the study's secondary endpoints will be performed using the mITT population. The analysis will also be performed using the PP population when appropriate.

Results will be summarized by mean, standard deviation, median, minimum and maximum of continuous variables; and by number and frequency (with percentages) of categorical variables.

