3. INTRODUCTION

This statistical analysis plan (SAP) describes the planned statistical methods to be used during the reporting and analysis of data collected under the Clinical Investigation Protocol entitled *Safety and Feasibility of Endoscopic Application of a Novel Therapy for Duodenal Mucosal Regeneration in the Treatment of Type II Diabetes (REGENT-1-US Study)*, Doc. No. 346. This SAP should be read in conjunction with the study protocol and case report forms (CRFs).

The REGENT-1-US study is a multicenter, open-label, treatment-only study conducted in Australia. The study is designed to assess the feasibility and preliminary safety of the Endogenex device for endoscopic duodenal cellular regeneration in patients with type 2 diabetes (T2D) inadequately controlled on glucose-lowering medications. The protocol enrolled patients who were treated with non-insulin glucose-lowering agents; a tabulation of the treatment and number of patients is presented below.

Device Generation 1 / 600 Volts / Single Treatment (n)	Device Generation 1 / 600 Volts / Double Treatment (n)	Device Generation 2 / 750 Volts / Double Treatment (n)	All Patients (n)
3	7	10	20

This plan is developed for analysis and reporting of the 48-week follow up data. The SAP may be revised in the future to address additional follow up data analysis beyond 48 weeks, if necessary.

Patients are considered enrolled in the study once the patient has passed endoscopic screening and proceeded to the Index procedure. **Screen failures** are defined as patients who consented to participate in the clinical study and started the screening tests specified by the protocol but are not subsequently enrolled into the study. Procedure success was defined as at least 6cm of duodenum was successfully treated.

The following analysis populations are defined for the presentation of the results from this study: *Intent-to-Treat* (ITT), *Full Analysis Set* (FAS) [referred to in the study protocol as the modified Intent-to-Treat (mITT) population], *Per-Protocol* (PP) and *Completed Cases* (CC). (Ref. Section 11.3 of the study protocol).

The primary and secondary safety analyses will be performed using the ITT population. The primary effectiveness analyses will be performed using the FAS population. The Per-Protocol population and Completed-Cases population will be used for the sensitivity analyses of the primary and secondary effectiveness endpoints.

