6. ANALYSIS POPULATIONS

Patients will be considered enrolled in the study once the patient has passed endoscopic screening. Screen failures are defined as patient who consented to participate in the clinical study and started the screening tests specified by the protocol but are not subsequently enrolled in the study.

The primary and secondary safety analyses will be performed using the ITT. The primary effectiveness analyses will be performed using the FAS population. The Per-Protocol population and Completed-Cases population will be used for the sensitivity analyses of the primary and secondary effectiveness endpoints.

Intent-to-Treat: The Intent-to-Treat population includes all enrolled patients, regardless of the patient having received the target treatment (at least 6cm of duodenum treated). The point of enrollment occurs when a patient has provided written informed consent and an energy delivery has been attempted during the index procedure.

Full Analysis Set: The FAS population consists of the ITT population patients who received the target treatment (at least 6 cm of duodenum treatment) and that have at least one post-treatment follow-up examination.

Per-Protocol: The Per-Protocol population is a subset of the FAS population and includes all patients who received the target treatment, do not have any major eligibility violations, and maintained stable glucose-lowering medications for 24 weeks post-procedure. The definition of what constitutes a major eligibility violations will be established before the study database is locked.

Completed Cases: The Completed Cases population is a subset of the Per-Protocol population and includes all patients who received the target treatment, do not have any major eligibility violations, and maintained stable glucose-lowering medications for 24 weeks post-procedure, and completed the final Week 48 End of Study Visit.

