9. ENDPOINTS ANALYSES

There is a single primary endpoint and 18 secondary endpoints. Based on the feasibility nature of this study, there are no formal hypothesis tests.

Primary Endpoint

The primary endpoint of the study is predicated on safety; the distribution of this endpoint is binary. The primary population for analysis of this endpoint will be the ITT population.

Proportion of patients experiencing one or more device- or procedure-related serious adverse events at 12 weeks post-procedure.

All device-related or procedure-related serious adverse events from the start of the study procedure through relative study day 84 will be used in the tabulation.

The secondary endpoints are listed below:

First Secondary Endpoint

The distribution of this endpoint is binary. The primary population for analysis of this endpoint will be the FAS population.

Procedure success: defined as successful treatment of at least 6 cm of duodenum segment.

Immediately following the study procedure, a determination will be made regarding treatment of ≥ 6 cm of the duodenum. Patients who fail to have ≥ 6 cm of the duodenum treated, for any reason, will be counted as not having achieved **Procedure Success**.

Second Secondary Endpoint

The distribution of this endpoint is continuous. The primary population for analysis of this endpoint will be the FAS population.

Procedure time: defined as the time between the Endogenex catheter insertion and the catheter removal.

Procedure Time will be reported in minutes.

Third Secondary Endpoint

The distribution of this endpoint is continuous. The primary population for analysis of this endpoint will be the FAS population.

Change from baseline (post-baseline minus baseline) in HbA1c reported for each pre-specified study visit.

The pre-specified study visits where HbA1c is recorded is Week 4, 12, 24, 36, 48.

Fourth Secondary Endpoint

The distribution of this endpoint is continuous. The primary population for analysis of this endpoint will be the FAS population.

Change from baseline (post-baseline minus baseline) in Fasting plasma glucose (FPG) reported for each pre-specified study visit.

The pre-specified study visits where FPG is recorded is Week 4, 12, 24, 36, 48.

Fifth Secondary Endpoint

The distribution of this endpoint is continuous. The primary population for analysis of this endpoint will be the FAS population.

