9.2. Analysis of the Secondary Effectiveness Endpoints

Endpoints have been classified relative to their distribution (binary, multinomial, or continuous), and the number of times the variable was recorded.

Binary Variable Assessed at a Single Time Point (3 endpoints):

- **Secondary Endpoint:** Procedure success: defined as successful treatment of at least 6 cm of duodenum segment.
- **Secondary Endpoint:** Proportion of treated patients with an HbA1c improvement of $\geq 0.5\%$ from baseline at 24 weeks (24 week score minus baseline score).
- **Secondary Endpoint:** Proportion of treated patients with an HbA1c improvement of $\geq 0.5\%$ from baseline at 24 weeks maintained at 48 weeks.

For each set of results for each Comparison Set, the following 2 research questions will be addressed. Results will be presented using the Level 1 tables b through e.

For the endpoints measured on a binary scale, what are the overall estimates in the FAS population.

For the endpoints measured on a binary scale, is there a difference in the estimates in the FAS population based on the generation of the device, voltage, and single vs. double treatment?

Multinomial Variable Assessed at a Single Time Point (1 endpoint):

- **Secondary Endpoint:** Proportion of patients that have a change in glucose-lowering medication usage from baseline.

For each set of results for each Comparison Set, the following 2 research questions will be addressed. Results will be presented using the Level 1 tables b through e.

For this endpoint measured on a multinomial scale, what are the overall estimates in the FAS population.

For this endpoint measured on a multinomial scale, is there a difference in the estimates in the FAS population based on the generation of the device, voltage, and single vs. double treatment?

Continuous Variable Assessed at a Single Time Point (3 endpoints):

- **Secondary Endpoint:** Procedure time: defined as the time between the Endogenex catheter insertion and the catheter removal.
- **Secondary Endpoint:** Change in liver enzyme from baseline at 24 weeks [Alanine Aminotransferase (ALT)].
- **Secondary Endpoint:** Change in liver enzyme from baseline at 24 weeks [Aspartate Aminotransferase (AST)].

For each set of results for each Comparison Set, the following 2 research questions will be addressed. Results will be presented using the Level 1 tables b through e.

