For each endpoint measured on a continuous scale, is there a difference in the estimates in the FAS population based on the generation of the device, voltage, and single vs. double treatment assessed over time?

The list of the top-line tables to be generated are presented below:

Table 14.4.1 entitled *Overall Summary of Procedure Success and Procedure Time (FAS Population)*

Table 14.4.2 entitled *Overall Summary of HbA1C, Fasting plasma glucose (FPG), Insulin-resistance by HOMA-IR, and Post-prandial plasma glucose (PPG) by Visit (FAS Population)*

Table 14.4.3 entitled *Overall Summary of Beta Cell Function by Visit (FAS Population)*

Table 14.4.4 entitled *Overall Summary of HbA1c improvement ≥ 0.3 points by Visit (FAS Population)*

Table 14.4.5 entitled *Overall Summary of Percent Change in Body Weight by Visit (FAS Population)*

Table 14.4.6 entitled *Overall Summary of Glucose-Lowering Medications by Visit (FAS Population)*

Table 14.4.7 entitled *Overall Summary of Liver Enzymes and Lipids by Visit (FAS Population)*

Table 14.4.8 entitled *Overall Summary of Blood Pressure Measurements by Visit (FAS Population)*

Table 14.4.9 entitled *Overall Summary of Continuous Glucose Monitoring (CGM) by Visit (FAS Population)*

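### Procedure success (at least 6 cm treated) is analysed only in patients who had at least 6 cm treated, so the planned rate is 100% whatever the device does

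*SAP*

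**What the plan says.** The first secondary endpoint in SAP Section 9 is procedure success, meaning at least 6 cm of duodenum treated. Its population is given as: "The distribution of this endpoint is binary. The primary population for analysis of this endpoint will be the FAS population". The same entry sets a failure rule for patients who do not reach the length: "6 cm of the duodenum treated, for any reason, will be counted as not having achieved" procedure success.

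SAP Section 6 (and Section 3 in the same terms) defines the analysis set: "The FAS population consists of the ITT population patients who received the target treatment (at least 6 cm of duodenum treatment"), with at least one post-treatment follow-up examination as a further condition. The Per-Protocol set is a subset of the FAS, and Completed Cases is a subset of Per-Protocol.

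SAP Section 9.2 keeps to the FAS for the overall estimate and for the group comparison ("For the endpoints measured on a binary scale, is there a difference in the estimates in the FAS population"). The only table listed for the endpoint is "Overall Summary of Procedure Success and Procedure Time (FAS Population").

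The protocol follows the same route. Section 11.4.3 states: "The primary analysis of the study's secondary endpoints will be performed using the mITT population". Section 3 lists procedure success among those endpoints, and Section 11.3 says: "The mITT population consists of the ITT population participants who received the target treatment (at least 6 cm of duodenum treatment").

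**The concern.** The condition that makes a patient a success is also the condition for entering the denominator. A success rate computed that way is fixed before any patient is treated. The failure rule quoted above shows that the authors meant failed procedures to count, but the choice of population means the rule can never apply to anyone.

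SAP Section 4.1 lists technical feasibility first among the secondary objectives, and procedure success is one of the two endpoints that serve it. A reported success rate of 100% would read as evidence about the device when it is a consequence of the definitions. The planned comparison by device generation, voltage and single or double treatment would set 100% against 100%.

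The follow-up condition adds a smaller problem. Success is determined immediately after the procedure, yet a treated patient with no later examination would also drop out of the analysis. Procedure time, the other feasibility endpoint, is not fixed by construction, but its FAS summary leaves out incomplete procedures.

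**Working it through.** **Logic.** Let S be the patients with at least 6 cm treated.

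- Endpoint (SAP 9): success means membership of S.
- FAS (SAP 3 and 6): ITT patients in S with at least one follow-up examination. So the FAS lies inside S.
- Planned estimate: number of FAS patients in S, divided by number in FAS = n/n = 100%. This holds in every device group.
- Per-Protocol and Completed Cases lie inside the FAS, so the sensitivity analyses also give 100%.
- Every group difference is exactly 0. A logistic comparison would have a constant outcome and could not be estimated.

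The documents state no expected success rate or power, so there is no planned figure to reproduce. The group sizes in SAP Section 3 do add up: 3 + 7 + 10 = 20.

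**Size.** Inputs: N = 20 (SAP 3 and 5.3); exact intervals (SAP 7); two-sided 95%, the level SAP 10.1.3 gives for adverse events, assumed here. The failure counts are assumptions, and follow-up is taken as complete. Intervals are Clopper-Pearson; for n successes out of n the lower limit is 0.025^(1/n), for example 0.025^(1/20) = 83.2%.

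| Group | Assumed failures | ITT | FAS |
|---|---|---|---|
| All, N = 20 | 0 | 20/20 = 100% (83.2 to 100) | 20/20 = 100% (83.2 to 100) |
| All, N = 20 | 1 | 19/20 = 95.0% (75.1 to 99.9) | 19/19 = 100% (82.4 to 100) |
| All, N = 20 | 2 | 18/20 = 90.0% (68.3 to 98.8) | 18/18 = 100% (81.5 to 100) |
| All, N = 20 | 4 | 16/20 = 80.0% (56.3 to 94.3) | 16/16 = 100% (79.4 to 100) |
| 750 V, N = 10 | 2 | 8/10 = 80.0% (44.4 to 97.5) | 8/8 = 100% (63.1 to 100) |

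In the FAS column the interval reflects only how many patients are left.

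**Chance that it matters.** With true success rate p, the chance of at least one failure in 20 is 1 − p^20. For assumed p of 95%, 90% and 80% this is 64%, 88% and 99%. The FAS estimate would hide each such failure.

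**The ITT denominator.** The SAP gives several enrolment points, and they do not agree:

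- Section 3, opening text: "Patients are considered enrolled in the study once the patient has passed endoscopic screening and proceeded to the Index procedure".
- Section 5.1: attempted catheter insertion.
- Section 6, opening text: passing endoscopic screening.
- ITT paragraphs in Sections 3 and 6: attempted energy delivery, as in Protocol 5.3.
- Section 10: start of endoscopic screening.

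The choice matters here. A patient in whom the catheter was inserted but no energy delivery was attempted is a technical failure under one definition and is not in the study under another.

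**The case against.** The strongest case is that failures would not vanish from the report. SAP Section 7 says in general that results recorded once use Level 1 displays on ITT, and procedure success is recorded once. SAP 8.4 plans an ITT table of index-procedure details, SAP 8.1 plans patient accounting by analysis population with population flags in the listings, and all data are listed. With 20 patients, a reader could subtract FAS from ITT. These citations are accurate. However, none of them assigns ITT to this endpoint or specifies an ITT success rate, and the content of the index-procedure table is not set out. ITT minus FAS also mixes failures with patients who had no follow-up. All the endpoint-specific text says FAS.

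Second, Protocol Appendix 4, Section 1 reports success in all of the first 27 patients, so there may be no failures to hide. The exact interval for 27/27 is 87.2 to 100%, which leaves a failure rate of up to 12.8% open. By the sequence in Protocol 4.1 those patients would have been on the first-generation catheter, whereas 10 of the SAP's 20 are on the second.

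Third, this is a secondary endpoint in a small study without formal testing, and the primary safety endpoint uses ITT. That is true and limits the reach of the defect. It does not make the planned estimate informative.

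Fourth, the protocol sentence is a blanket rule that does not name procedure success, and the SAP cites protocol Doc. No. 346 while the protocol supplied is No. 196. The blanket rule still covers the endpoint because Section 3 lists it, and the SAP's defect stands without the protocol.

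**Conclusion.** The concern holds. As written, the procedure success analysis can return only 100%, overall, by group and in both sensitivity sets. This follows from the definitions alone and needs no outside assumption. How far the reported rate would be from the ITT rate depends on the number of failures, which is unknown: none with 0 failures, 10 percentage points with 2 of 20, and 20 points with 4 of 20, assuming complete follow-up. If every procedure succeeds, ITT also gives 100%, and only then is that figure evidence about the device. The endpoint needs correcting before the analysis is run. The procedure-time point is secondary, and the conclusion does not rest on it.

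**What to change.** 1. Settle one enrolment and ITT definition across SAP Sections 3, 5.1, 6 and 10. Attempted energy delivery is already common to the SAP's ITT paragraphs and Protocol 5.3. If it is kept, also report how many patients had catheter insertion attempted but no energy delivery attempted.
2. In SAP Sections 9 and 9.2, in the procedure success table and in Protocol 11.4.3 (or the matching section of the protocol that governs this SAP), analyse procedure success in ITT, overall and by group. Count less than 6 cm as failure and give an exact 95% interval. Renumber that table, because SAP 9.1 already uses 14.4.1 for the primary safety endpoint.
3. Report procedure time in ITT alongside the FAS summary, with incomplete procedures identified.
4. Keep FAS/mITT for the glycaemic endpoints.

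For the endpoint itself the cost is wording: no new data are needed, and index-procedure data are already tabulated on ITT. Reconciling the enrolment definitions touches four SAP sections and should be done before database lock. The sponsor accepts that the reported rate falls below 100% if any procedure fails.

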6.2.1 Background Glucose-Lowering Medications

Eligible participants must be on one to four non-insulin glucose-lowering medication(s) without a severe hypoglycemic event within the past six months of the screening visit.

Participant's background medication will be kept stable (no change in medication or dose) for at least 12 weeks prior to the Baseline Visit.

Peri-procedurally, the dose of medications with hypoglycemic risks will be adjusted per guidelines provided in **Section 6.2.2**.

During the transitional diet period, participant's medication will be titrated to the background level and maintained stable until the Week 24 Visit has been completed. Medication and/or dose change necessary for managing hypoglycemia, hyperglycemia, or other safety concerns is permitted. Reason for the medication change must be documented on eCRF.

Following the Week 24 Visit, participants will be managed according to the current (2020) guidelines of the American Diabetes Association² and their glucose-lowering medications will be optimized as necessary to reach an HbA1c target of 7%.

Background medications are non-investigational products. They should be used in accordance with standard of care and their approved labeling. They will not be provided by the sponsor except if required by local regulations.

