6.2.3 Rescue Criteria

Participant with a fasting glucose > 270 mg/dL, confirmed by repeat measure, and/or associated with symptoms of abdominal pain, nausea, vomiting or dehydration will trigger the recommendation to be

evaluated by the treating physician and the consideration of intensification of background glucose-lowering medication and/or initiation of new medication.

The above criteria are provided as a guideline. Investigators should always exercise his/her clinical judgement to protect participant's safety.

Medication changes and reasons for the changes will be documented on the eCRFs. Medications used to manage hyperglycemia are non-investigational and will not be provided by the sponsor.

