4.2.1. Secondary Endpoints

First Secondary Endpoint: Procedure success: defined as successful treatment of at least 6 cm of duodenum segment.

Second Secondary Endpoint: Procedure time: defined as the time between the Endogenex catheter insertion and the catheter removal.

Third Secondary Endpoint: Change from baseline (post-baseline minus baseline) in HbA1c reported for each pre-specified study visit.

Note: The estimates will be derived using a mixed model repeated measure procedure; the 24 week result will be the principal time point of interest.

Fourth Secondary Endpoint: Change from baseline (post-baseline minus baseline) in Fasting plasma glucose (FPG) reported for each pre-specified study visit.

Note: The estimates will be derived using a mixed model repeated measure procedure; the 24 week result will be the principal time point of interest.

Fifth Secondary Endpoint: Change from baseline (post-baseline minus baseline) in Insulin-resistance by HOMA-IR reported for each pre-specified study visit.

Note: The estimates will be derived using a mixed model repeated measure procedure; the 24 week result will be the principal time point of interest.

Sixth Secondary Endpoint Part 6a: Change from baseline (post-baseline minus baseline) in Post-prandial plasma glucose (PPG) based on mixed meal tolerance test (MMTT) reported for each pre-specified study visit.

Note: The estimates will be derived using a mixed model repeated measure procedure; the 12 week result will be the principal time point of interest.

Sixth Secondary Endpoint Part 6b: Change from baseline (post-baseline minus baseline) in beta cell function based on mixed meal tolerance test (MMTT) reported for each pre-specified study visit.

Note: The estimates will be derived using a mixed model repeated measure procedure; the 12 week result will be the principal time point of interest.

Sixth Secondary Endpoint Part 6c: Change from baseline (post-baseline minus baseline) in the disposition index based on mixed meal tolerance test (MMTT) reported for each pre-specified study visit.

Note: The estimates will be derived using a mixed model repeated measure procedure; the 12 week result will be the principal time point of interest.

Seventh Secondary Endpoint: o Time in range, glucose variability by continuous glucose monitoring (CGM)

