7.3. Handling of Missing Data

7.3.1. Missing and Censored Data

All tabulations and analyses will be based on the observed data without imputation, with the exception of dates.

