Proportion of treated patients with an HbA1c improvement of $\geq 0.5\%$ from baseline at 24 weeks (24 week score minus baseline score). Patients who fail to have HbA1c improvement of ≥ 0.5 points from baseline, for any reason, will be counted as not having achieved this endpoint.

Ninth Secondary Endpoint

The distribution of this endpoint is binary. Proportion of treated patients who achieve a HbA1c improvement of $\geq 0.5\%$ or more at 24 weeks from baseline and maintained at 48 weeks. Patients who fail to maintain HbA1c improvement $\geq 0.3\%$ at 48 weeks, for any reason, will be counted as not having achieved this endpoint. Patients who fail to achieve a HbA1c $\geq 0.5\%$ at 24 weeks will be excluded from the tabulation. The primary population for analysis of this endpoint will be the FAS population.

Proportion of treated patients with an HbA1c improvement $\geq 0.5\%$ from baseline at 24 weeks maintained at 48 weeks.

Tenth Secondary Endpoint: The distribution of this endpoint is continuous. The primary population for analysis of this endpoint will be the FAS population. Change in weight from baseline (post-baseline minus baseline) by visit. Weight change will be reported in both kilograms and %TBWL.

Eleventh Secondary Endpoint: Change in glucose-lowering medication usage.

Twelfth Secondary Endpoint: The distribution of this endpoint is continuous. The primary population for analysis of this endpoint will be the FAS population. Change in liver enzyme from baseline at 24 weeks (post-baseline minus baseline) for Alanine Aminotransferase (ALT).

Thirteenth Secondary Endpoint: The distribution of this endpoint is continuous. The primary population for analysis of this endpoint will be the FAS population. Change in liver enzyme from baseline at 24 weeks (post-baseline minus baseline) for Aspartate Aminotransferase (AST).

Fourteenth Secondary Endpoint: The distribution of this endpoint is continuous. The primary population for analysis of this endpoint will be the FAS population. Change from baseline in blood pressure by visit (systolic and diastolic run separately).

Fifteenth Secondary Endpoint: The distribution of this endpoint is continuous. The primary population for analysis of this endpoint will be the FAS population. Change in lipid profile from baseline by visit: total cholesterol

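### The SAP has no rule for glucose-lowering intensification before Week 24, so the FAS can credit a drug effect as response and no planned analysis counts it as failure

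*SAP*

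**What the plan says.** For HbA1c and FPG change, SAP 4.2.1 states: "The estimates will be derived using a mixed model repeated measure procedure; the 24 week result will be the principal time point of interest". SAP 5.1 and Protocol 6.2.1 hold background drugs at the pre-procedure dose until Week 24 and allow optimisation afterwards.

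The hold is not absolute. Protocol 6.2.1: "Medication and/or dose change necessary for managing hypoglycemia, hyperglycemia, or other safety concerns is permitted". The rescue guideline in Protocol 6.2.3 leads to "the consideration of intensification of background glucose-lowering medication and/or initiation of new medication" and is not confined to the period after Week 24. Both sections require the change and its reason to be recorded on the eCRF.

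The eighth secondary endpoint (SAP 9) is a binary Week-24 response: patients whose HbA1c does not improve by at least 0.5 points, "for any reason, will be counted as not having achieved this endpoint". It is analysed in the FAS, which SAP 6 defines by length of duodenum treated and at least one follow-up, with no medication condition. SAP 7.3.1 adds: "All tabulations and analyses will be based on the observed data without imputation, with the exception of dates".

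The sensitivity sets are Per-Protocol, limited to patients who "maintained stable glucose-lowering medications for 24 weeks post-procedure", and Completed Cases, a subset of Per-Protocol. Change in glucose-lowering medication is a separate endpoint (the eleventh) and is not linked to HbA1c response.

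**The concern.** A participant whose glucose is not controlled after the procedure may have a drug added or increased at, say, Week 14. If HbA1c at Week 24 is then 0.5 points or more below baseline, the observed value makes that participant a responder in the FAS. The any-reason clause of the eighth endpoint covers those who miss the threshold; it does not ask how the threshold was reached.

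In PP and Completed Cases the same participant disappears from numerator and denominator alike. So no planned analysis keeps an intensified participant in the denominator as a non-responder.

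The study has one arm, so no control group under the same rescue practice can offset the drug effect. The efficacy output consists of estimates, and SAP 3 expects the analyses may be used in regulatory submissions and manuscripts. A reader of the Week-24 result will take it as response on stable drugs.

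**Working it through.** **Inputs.** N = 20, made up of 3 + 7 + 10 = 20 (SAP 3); the sum agrees. Response threshold 0.5 points (SAP 9). The documents give no rescue rate, no HbA1c response after rescue and no rate of dose reduction, so there is no stated figure to reproduce. Assumed ranges: 0 to 4 of 20 intensified, with none or all of them reaching the threshold; 0 to 3 responders with reduced drugs; a drug effect of 0.5 to 1.0 HbA1c points.

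**Notation.** k = participants intensified before the Week-24 HbA1c; r = those of the k who reach the threshold; R = responders among the rest; d = responders whose drugs were reduced and who leave PP for that reason.

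- FAS as planned: (R + r)/N
- Intensification counted as non-response: R/N
- PP: (R − d)/(N − k − d)

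**Step 1, FAS.** The difference is (R + r)/N − R/N = r/N. Each such participant adds 1/20 = 5 points overall, and 1/3 = 33, 1/7 = 14 or 1/10 = 10 points within the three device groups. For r = 0 to 4 the overall difference runs from 0 to 20 points. It is never negative, and it is zero when r = 0.

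**Step 2, PP if only intensified participants are dropped (d = 0).** The difference from R/N is R·k/(N(N − k)). The low end is R = 6, k = 1: 6/(20 × 19) = 1.6 points. The high end is R = 11, k = 4: 44/(20 × 16) = 13.75 points. It is never negative.

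**Step 3, PP when reductions also break stability.** Take k = 2, r = 2, R = 10. The FAS rate is 12/20 = 60.0% (exact 95% interval 36.1 to 80.9). Counting intensification as non-response gives 10/20 = 50.0% (27.2 to 72.8). PP then depends on d:

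| d | PP | Rate |
|---|---|---|
| 0 | 10/18 | 55.6% |
| 1 | 9/17 | 52.9% |
| 2 | 8/16 | 50.0% |
| 3 | 7/15 | 46.7% |

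PP passes from above the 50.0% reference to below it, so its direction is not fixed.

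**Step 4, mean HbA1c change.** The shift in the observed FAS mean is (k/N) × drug effect: from 1/20 × 0.5 = 0.025 to 4/20 × 1.0 = 0.20 points. Participants kept in the FAS on reduced drugs can move the mean the other way.

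**Step 5, endpoint 9.** SAP 9 excludes participants who miss the Week-24 criterion from the sustained-response tabulation. In the Step 3 example, 12 FAS participants enter it as planned. Merely relabelling the 2 intensified participants as Week-24 failures would leave 10 and delete those 2. All 20 must stay in the denominator if they are to count as failures.

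**The case against.** A reader might infer that FAS and PP both overstate efficacy and err in the same direction. The documents do not support that. The FAS excess needs at least one intensified participant who reaches the threshold. PP requires stable drugs, not merely the absence of increases, and Protocol 6.2.1 and 6.2.2 also provide for reductions, so Step 3 can go either way. Likewise, a mean shift as large as 0.40 points would need 20% intensified and a 2.0-point drug effect (0.20 × 2.0); neither figure is in the documents.

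Rescue may also be rare. The guideline's fasting threshold is above 270 mg/dL, it leads only to evaluation and consideration of a change, and confirmed fasting values above 270 mg/dL since screening are an exclusion (Protocol 5.2, criterion 41). This stands as a limit on size. Against it, the guideline defers to clinical judgement, and Protocol 6.2.1 sets no glucose threshold for a permitted change.

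An estimate that includes later drug changes is a legitimate target, and against it the FAS rate is not biased. But the SAP names no target, and holding drugs fixed to Week 24 points to response on stable drugs.

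Efficacy is secondary and descriptive, with no formal hypothesis tests (SAP 9), so no error rate is at stake. Medication use is tabulated by visit (SAP 9.2, Table 14.4.6) and all data are listed, so the information is partly visible. It is not joined to response.

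Finally, the permitted-change text is in Protocol 196, whereas SAP 3 names REGENT-1-US, Doc. No. 346. SAP 5.1 differs from Protocol 196 on country, number of background drugs and baseline window. It does refer to a Section 6.2 for background medication, and its PP definition presupposes that some participants will not stay stable. The caveat stands.

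**Conclusion.** The gap holds; a fixed upward bias in both analyses does not. The SAP does not say how HbA1c or FPG measured after pre-Week-24 intensification is handled. Against response on stable drugs, the FAS responder rate can be too high by r/N: 5 points per intensified responder at N = 20, nothing if there are none. The net direction of PP and Completed Cases is undetermined, so agreement or disagreement with the FAS tells the reader nothing reliable about this problem.

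This rests on three assumptions: that the intended Week-24 target is response on stable drugs, that Doc. No. 346 carries a provision like that in Protocol 196, and that some intensification occurs. The counts above illustrate size and do not predict it. The point should be settled before database lock; it does not threaten the primary safety endpoint.

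**What to change.** First confirm that Doc. No. 346 permits the same medication changes. Then, in SAP 9:

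- **Endpoint 8.** Beside the observed-data result, add an FAS analysis that counts as a non-responder anyone whose glucose-lowering therapy was increased above, or added to, the pre-procedure regimen before the Week-24 HbA1c. Return to the pre-procedure dose does not count. This reference is needed because the Protocol Summary returns sulfonylureas and meglitinides to that dose after the transitional diet, and a looser flag would fail true responders.
- **Endpoint 9.** Report the same analysis with all FAS participants in the denominator, so that intensified participants count as failures and are not excluded.
- **HbA1c and FPG change at Week 24.** Show the repeated-measures estimate with post-intensification values set aside beside the all-observed estimate.
- **Medication changes.** Report increases and decreases separately, by response status.

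The cost is one SAP rule, one derived flag and a few more tables. Protocol 196 already requires changes and reasons on the eCRF, and no clinical rule is altered. The responder rate may look less favourable.
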